7.6 APPROPRIATENESS OF MEASUREMENTS

The assessments that will be made in this study are standard, and are generally recognized as reliable, accurate, and relevant.

8. STUDY TERMINATION/COMPLETION

8.1 STUDY COMPLETION

A subject will be considered to have completed the study if she has completed the 12-week treatment period.

8.2 REMOVAL OF SUBJECTS FROM THE STUDY OR TREATMENT

Subjects have the right to withdraw from the study at any time for any reason, including personal reasons. A subject can withdraw without giving a reason. This will not affect the subject's future care. The Investigator should however try to find out why a subject has withdrawn from the study and document the reason for withdrawal in the source documents and on the eCRF.

A subjects **may** be withdrawn from the study or treatment in the event of:

- An AE, including clinically significant new or worsening existing conditions as judged by the Investigator (documented on the AE Form of the eCRF);
- Subject request (subject moved, schedule conflicts, etc);
- A major protocol violation which would confound interpretation of the results;
- Other: this reason should only be used if the reason for withdrawal is not better accounted for by one of the other categories.

A subjects **must** be withdrawn the study or treatment in the event of:

- Withdrawal of informed consent;
- Lost to follow-up;
- For safety reasons, it being in the best interest of the subject that she be withdrawn, in the Investigator's opinion;
- Development of a medical condition that requires concomitant treatment with a prohibited therapy (see Section [6.2](#));
- Breaking of the randomization code during administration of the study drug by the Investigator or by a member of his/her staff. If the code is broken by the Sponsor, for safety reporting purposes, the subject may remain in the study.
- QT interval corrected according to Fridericia's formula (QTcF) increases to >500 ms, as confirmed by 2 additional ECG recordings obtained within 10 minutes of the initial recording;
- Confirmed decrease in thrombocytes below 75.000, which does not normalize after 7 days;
- ALT or AST >8x ULN;
- ALT or AST >5x ULN for more than 2 weeks;
- ALT or AST >3x ULN and total bilirubin >2x ULN;
- ALT or AST >3xULN with the appearance of fatigue, nausea, vomiting, right upper quadrant pain or tenderness, fever, rash, and/or eosinophilia (>5%).

See [Attachment 6](#) for the procedure to follow in case of suspected drug-induced liver injury (DILI).

In the event that a subject is withdrawn from the study, the monitor and Sponsor should be informed: in case of withdrawal due to an SAE (for details on AE reporting see Section 10), the Sponsor should be notified within 24 hours; in case of withdrawal for other reasons, the Sponsor should be notified within 2 days from the event.

If there is a medical reason for withdrawal, the subject will remain under the supervision of the Investigator until satisfactory health has returned.

Subjects who are withdrawn from the study prior to completion of the scheduled study procedures for any reason (AE, withdrawal of consent, etc.) should be invited to complete the assessments as much as possible: as long as the subject consents, all relevant assessments of the day on which the subject withdrew from the study should be completed, at least those related to safety, and the subject should come for a safety follow-up visit 2-3 weeks after the last intake of study drug. In case of an AE, the appropriate follow-up will be done.

Subjects who are withdrawn from the study will not be replaced.

Study drugs assigned to a withdrawn subject must not be assigned to another subject.

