5.8 TREATMENT COMPLIANCE

Study drugs will be dispensed to the subjects at Visits 2, 3, and 4 (one bottle containing 68 capsules at every visit).

On days of visits during the treatment period, the morning dose of study drug will be taken at the clinical site, under the supervision of the clinical staff. All other study drug intakes (evening dose and morning dose on all days without visits) will be done at home. When taking their study drug at home, subjects will be asked to record their home study drug intake in the ePRO diary. Subjects will also be asked to return all unused study drugs.

Compliance towards study drug intake will be assessed by counting returned dosage units in addition to ePRO entries upon study drug intake. Any discrepancies between returned dosage units and dosing in the ePRO diary will be discussed with the subject for whom a discrepancy was seen and recorded in the source documents and the eCRF. If a subject demonstrates continued non-compliance with study drug dosing, despite educational efforts, the Investigator should contact the Sponsor to discuss withdrawal of the subject from the study.

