9. STATISTICAL METHODS

9.1 STATISTICAL ANALYSIS

All statistical analyses will be performed by SGS Life Science Services using SAS® (SAS Institute Inc., Cary, NC, USA; version 9.2 or higher) software for statistical computations.

All statistical methods shall be detailed in a Statistical Analysis Plan (SAP) that will be finalized before database lock.

All data collected in this study will be documented using summary tables, figures, and subject data listings.

Descriptive statistics will include number of subjects, (arithmetic) mean, standard deviation (SD), median, minimum and maximum, and a 95% confidence interval (CI). Frequency tabulations will show counts and percentages.

All statistical tests will be interpreted at the 5% significance level (2-tailed).

An interim analysis on the primary endpoint, DEXA parameters and safety data will be performed once the first 16 subjects will have completed 12 weeks of treatment and the follow-up visit (or have discontinued earlier). The final analysis will be performed once all subjects will have completed 12 weeks of treatment and the follow-up visit (or have discontinued earlier).

The following populations will be considered for analysis:

- Safety population: defined as all subjects who are randomized into the study and received at least one dose of the study drug. All safety tables and listings will be based on the safety population.
- Intent-to-treat (ITT) population: defined as all randomized subjects who received at least one dose of the study drug and who have post-baseline efficacy data. Unless specified otherwise, the ITT population will be used for efficacy analysis.
- Per-protocol (PP) population: defined as a subset of the ITT population, excluding those subjects who have major protocol deviations and violations. All deviations and violations will be reviewed prior to database lock and classified as either minor or major.

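### Section 8.2 permits withdrawal from the study for a major protocol violation, although the PP set already handles such violations; a violator withdrawn before Week 12 then has no observed primary endpoint in the ITT analysis

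*Protocol*

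**What the plan says.** Section 8.2 has two lists, one of reasons for which a subject may be withdrawn from the study or treatment and one of reasons for which she must be. The permissive list includes "A major protocol violation which would confound interpretation of the results". Safety has its own entries; the mandatory list contains, for example, "For safety reasons, it being in the best interest of the subject that she be withdrawn, in the Investigator's opinion". For the time after a withdrawal, given her consent, the section asks that "all relevant assessments of the day on which the subject withdrew from the study should be completed, at least those related to safety", followed by one safety visit two to three weeks after the last dose. Withdrawn subjects are not replaced.

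Section 5.8 covers non-compliance with dosing that continues despite education: "the Investigator should contact the Sponsor to discuss withdrawal of the subject from the study".

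Section 9.1 describes how violations enter the analysis. "All deviations and violations will be reviewed prior to database lock and classified as either minor or major". The PP set is "defined as a subset of the ITT population, excluding those subjects who have major protocol deviations and violations". The ITT set is "defined as all randomized subjects who received at least one dose of the study drug and who have post-baseline efficacy data", and "Unless specified otherwise, the ITT population will be used for efficacy analysis".

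The primary endpoint (Section 7.4.2.1) is the change from baseline to Week 12 in weekly Hot Flash Score, taken from the diary. Section 9.1.4 leaves the imputation of missing scores to the SAP.

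**The concern.** Whether a violation confounds interpretation is a question for the analysis. The protocol has an instrument for it, the PP set, which can be applied after the data are in and can be reversed. Ending study participation for the same reason acts earlier and cannot be undone: if the pre-lock review later grades the violation as minor, the diary weeks after withdrawal still do not exist.

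The ITT set is meant to keep violators and non-compliers with the outcomes they actually had. If some leave the study because they violated the protocol, the ITT analysis loses those outcomes, and its comparison with the PP analysis says less. Non-adherence can depend on arm, for instance through poor tolerability on active or poor relief on placebo, so the loss can bias the estimate as well as widen its interval. Section 9.2 intends the results as the basis for designing and powering a Phase IIb study, so a distorted effect estimate could carry over into that sample size.

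**Working it through.** The protocol states no power, effect size, SD, dropout rate or violation rate, so there is no figure of its own to reproduce. The check is first textual, then an illustration of scale.

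**What happens to a withdrawn violator**

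1. Is she in the ITT set? One dose and some post-baseline efficacy data suffice. The diary is filled in at least twice daily, so almost anyone withdrawn after the first days qualifies.
2. Does she have an observed Week 12 score? Section 8.2 asks for withdrawal-day assessments and a safety visit tied to the last dose. Suppose, generously, that the diary runs on until that visit. It would then reach Week 12 only if the last dose fell at about Week 9 or later (12 − 3 = 9; 12 − 2 = 10). Earlier withdrawals have no Week 12 diary.
3. What if only treatment is stopped? The wording allows this, but no off-treatment schedule to Week 12 is set out.
4. What replaces the missing score? An SAP rule that is not shown here.

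**Possible bias (assumed rates)**

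Let a share *s* of the active arm be removed, let those subjects retain a fraction *r* of the drug effect, and let the remaining subjects be analysed without imputation. The full-arm effect is (1 − *s*(1 − *r*)) times the effect in those who remain, so

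inflation = 1 / (1 − *s*(1 − *r*)) − 1.

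| *s* | *r* = 0 | *r* = 0.5 |
|---|---|---|
| 5% | 1/0.95 − 1 = 5.3% | 1/0.975 − 1 = 2.6% |
| 10% | 1/0.90 − 1 = 11.1% | 1/0.95 − 1 = 5.3% |
| 15% | 1/0.85 − 1 = 17.6% | 1/0.925 − 1 = 8.1% |

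In SD units for either arm: if a share *w* is removed and differs from the rest by *k* SD, that arm's mean shifts by *w* × *k*. This gives 0.10 × 0.5 = 0.05 SD, or 0.20 × 1.0 = 0.20 SD.

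**Possible loss of precision (assumed rate, equal in both arms)**

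Inputs: 40 per arm (Section 5.5) and 5% two-sided (Section 9.1). The half-width of the 95% CI in SD units is t(0.975, 2n − 2) × √(2/n).

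- n = 40: 0.445 SD
- n = 36 (10% lost): 0.470 SD, an increase of 0.025 SD

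The effect detectable with an assumed 80% power, (1.960 + 0.842) × √(2/n), goes from 0.626 to 0.660 SD. At 0.626 SD, power falls from 80.0% to 75.7%.

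At such rates the loss of precision is small. What matters more is removal that differs by arm.

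**The case against.** The strongest reply is that the rule is discretionary and that its use is unknown. Section 8.2 says subjects may be withdrawn, and from the study or from treatment. A reader might infer that violators' Week 12 data are lost as a matter of course. The text does not support that: data are lost only for violators actually withdrawn from the study before Week 12. This stands.

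A reader might also see a contradiction in timing: violations judged at the site during the trial but graded only before database lock. The documents do not go that far. The bullet names no decision-maker, Section 5.8 brings in the sponsor, and a review before lock does not exclude ongoing review. A conduct rule and an analysis-set rule can coexist. What remains is that the conduct rule pursues an analytic aim that the PP set already serves, and at the cost of data.

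Third, withdrawn subjects mostly remain in ITT, and the SAP may impute their scores. That is correct, so how far the estimate moves depends on rules not seen here. Imputation still does not supply the observed value.

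Fourth, the gap in follow-up affects every withdrawal reason, and 8.2 separately requires withdrawal when a condition needs a prohibited therapy. Removals by that route lie outside this point. The violation ground is different in that nothing about the subject's safety or consent requires her to leave.

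Finally, the study is an unpowered proof of concept with exploratory tests, and the 5.8 route is narrow: persistent non-compliance, and then only a discussion. Both lower the weight of the point.

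**Conclusion.** The point holds in a limited form. The protocol permits, without requiring, that a randomised subject leave the study for an analytic reason that Section 9.1 already handles through the PP set. A violator so withdrawn before Week 12 will generally have no observed primary endpoint, although she usually stays in ITT with imputation left to the SAP. If such removals differ by arm, the ITT estimate may shift toward a per-protocol one.

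The size cannot be derived from the documents. The range of 5.3% to 17.6% should not be read as an expected bias: it assumes that 5% to 15% of the active arm is removed and nobody on placebo, that those removed would have shown no drug effect, and that nothing is imputed. With half the effect retained, the range is 2.6% to 8.1%. An equal 10% loss in both arms widens the CI half-width by only 0.025 SD. The change is worth making because it is cheap and protects the default analysis set; the point does not put the trial's conclusions in doubt by itself.

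**What to change.** In Sections 8.2 and 5.8, state that a protocol violation or non-compliance alone does not end study participation. With the subject's consent, diary and scheduled visits continue to Week 12, she stays in ITT with her observed data, the event is documented as a deviation, and any exclusion is made only in the PP set at the review before database lock.

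Limit the change to study participation. Deleting the whole bullet from 8.2 would also remove a ground for stopping treatment, which is not the aim. The safety grounds and all decisions on study drug stay as written.

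The cost is wording in two sections, plus a few subjects with violations completing visits and diary entries already planned for them.

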8.3 STOPPING RULES OR DISCONTINUATION CRITERIA

The study may be stopped for any of the following reasons:

- If 2 or more subjects on the study drug are withdrawn from the study due to QTcF interval increases >500 ms, as confirmed by 2 additional ECG recordings obtained within 10 minutes of the initial recording;
- If 2 or more subjects on the study drug are withdrawn from the study due to a confirmed increase in ALT or AST >5x ULN for more than 2 weeks;
- If 2 or more subjects on the study drug are withdrawn from the study due to a confirmed decrease in thrombocytes below 75.000, which does not normalize after 7 days.

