2.0 INTRODUCTION

Hepatotoxicity is injury or damage to the liver that may be associated with impaired liver function (Navarro and Senior 2006). Drug-induced hepatotoxicity is one of the most common causes of termination of drug development, a major reason for refusal of market authorization and for restricted use, and the single most important cause of the withdrawal of market authorization for products (Björnsson 2006). Thus, drug-induced hepatotoxicity is a major concern during the discovery, development to post-authorization phases of the product life cycle (excerpted from Draft Guidance Document, Hepatotoxicity of Health Products, Ministry of Public Health, Canada, December 2010).

As stated in the United States Food and Drug Administration (FDA) "Guidance for Industry - Drug-Induced Liver Injury: Premarketing Clinical Evaluation"; hepatocellular injury (usually detected by serum aminotransferase elevations [AT]) can be caused by drugs that rarely, if ever, cause severe DILI (e.g., aspirin, tacrine, statins, and heparin), as well as by drugs that do cause such injury. The frequency of serum AT elevations also is not a good indicator of a potential for severe DILI because drugs such as tacrine (not a cause of severe DILI) can cause AT elevations in as many as 50 percent of patients. Very high levels of observed ATs may be a somewhat better indicator of potential for severe DILI, but the most specific indicator is evidence of altered liver function accompanying or promptly following evidence of hepatocellular injury.

The single clearest (most specific) predictor found to date of a drug's potential for severe hepatotoxicity, is the occurrence of hepatocellular injury (AT elevation) accompanied by increased serum total bilirubin (TBL) not explained by any other cause, such as viral hepatitis or exposure to other hepatotoxins, and without evidence of cholestasis, together with an increased incidence of AT elevations in the overall trial population compared to control. Increased plasma prothrombin time, or its international normalized ratio (INR), a consequence of reduced hepatic production of Vitamin K-dependent clotting factors, is another potentially useful measure of liver function that might suggest the potential for severe liver injury.

Recognition of the importance of altered liver function, in addition to liver injury, began with Hyman Zimmerman's observation that drug-induced hepatocellular injury (i.e., AT elevation)

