Site Guidance Document for Assessment of Potential DILI
accompanied by jaundice (i.e., TBL elevation) had a poor prognosis, with a 10 to 50 percent mortality from acute liver failure (in pretransplantation days) (Zimmerman 1978, 1999). This became known as "Hy's Law". This document describes the recommended process for monitoring and evaluation of subjects meeting the laboratory criteria for potential DILI defined as:

- an elevated alanine transaminase (ALT) or aspartate transaminase (AST) lab value that is greater than or equal to three times (3X) the upper limit of normal (ULN) and
- an elevated TBL lab value that is greater than or equal to two times (2X) ULN and
- at the same time, an alkaline phosphatase (ALP) lab value that is less than 2X ULN,

as a result of within-protocol-specific testing or unscheduled testing.

The protocol identifies these laboratory criteria for potential DILI as ECIs. ECIs are selected adverse experiences that must be reported to the Sponsor within 24 hours. The Principal Investigator should record these ECIs on the Adverse Experience Case Report Forms (CRFs) and complete pertinent adverse experience fields as outlined in the Data Entry Guidelines (DEGs).

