3.0 CLOSE OBSERVATION RECOMMENDATIONS

The following steps should be taken when a subject is observed to have an elevated AST or ALT lab value that is greater than or equal to 3X ULN and an elevated TBL lab value that is greater than or equal to 2X ULN and, at the same time, an ALP lab value that is less than 2X ULN, as a result of within-protocol-specific testing or unscheduled testing.

Initiate **close observation**, defined below, and continue performing **follow-up** to resolution.

Close observation is defined as follows:

- Repeat liver enzyme and serum bilirubin tests two (2) or three (3) times weekly. Frequency of retesting can decrease to once a week or less if abnormalities stabilize or study drug has been discontinued and the subject is asymptomatic.
- Obtain a more detailed history of symptoms and prior or concurrent diseases. (See Section 5).
- Obtain a history of concomitant medication use (including prescription and nonprescription medications, herbal and other dietary supplements), alcohol use, recreational drug use and special diets. (See Section 5 for details.)
- Obtain a history of exposure to chemical agents or other environmental toxins.

[figure not shown]

Site Guidance Document for Assessment of Potential DILI

- Obtain additional history and complete Stage 1 work-up to attempt to rule out other potential causes of the transaminase elevation, including but not limited to the following: acute viral hepatitis types A, B, C, D, and E; autoimmune or alcoholic hepatitis; non-alcoholic steatohepatitis (NASH); hypoxic/ischemic hepatopathy; and biliary tract disease. (See Section 5.5 for details.)
- Consider gastroenterology or hepatology consultation.

In general, treatment with study therapy should be stopped if the laboratory criteria for potential DILI are met. Please refer to the specific discontinuation criteria in the protocol as appropriate.

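### The only liver stopping rule in Section 8.3 does not count withdrawals for ALT/AST >8x ULN or for ALT/AST >3x ULN with total bilirubin >2x ULN, although Section 8.2 makes both mandatory.

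*Protocol*

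**What the plan says.** Section 8.2 of the protocol has a list of events after which a subject must be withdrawn. Four of them concern the liver:

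- "ALT or AST >8x ULN", with no duration condition;
- ALT or AST above 5x ULN lasting more than two weeks;
- "ALT or AST >3x ULN and total bilirubin >2x ULN", with no duration condition;
- ALT or AST above 3x ULN with listed symptoms, rash or eosinophilia.

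Section 8.3 gives three reasons for which the study may be stopped, each needing two or more subjects on study drug to have been withdrawn for the stated cause. They concern QTcF, liver and thrombocytes. The liver cause is a "confirmed increase in ALT or AST >5x ULN for more than 2 weeks".

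Attachment 6, section 2.0, names as the most specific predictor of severe hepatotoxicity "hepatocellular injury (AT elevation) accompanied by increased serum total bilirubin (TBL) not explained by any other cause". It adds two qualifiers: "without evidence of cholestasis, together with an increased incidence of AT elevations in the overall trial population compared to control". Its laboratory definition of potential drug-induced liver injury uses ALT or AST at or above 3x ULN, bilirubin at or above 2x ULN and "at the same time, an alkaline phosphatase (ALP) lab value that is less than 2X ULN". On reporting it says "ECIs are selected adverse experiences that must be reported to the Sponsor within 24 hours". Section 3.0 of the attachment adds: "In general, treatment with study therapy should be stopped if the laboratory criteria for potential DILI are met".

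**The concern.** The 8.3 count depends on why a subject was withdrawn. A subject above 8x ULN, or above 3x ULN with raised bilirubin, has to leave on that finding, before any two-week period can run. Her withdrawal reason is then one that 8.3 does not list. The liver rule therefore works against severity: the slower, milder course is counted and the more severe one usually is not.

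At stake is whether two severe liver cases, in a drug whose earlier human dosing lasted at most 21 days (Section 1.3) and is now given for 12 weeks, reach a defined point at which stopping the whole study is to be considered.

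**Working it through.** The plan states no figure on this point, so the check is a comparison of the two lists.

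**Step 1. Individual criteria against study-level criteria.**

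| Section 8.2 mandatory withdrawal | In Section 8.3? |
|---|---|
| QTcF >500 ms, confirmed | yes |
| Thrombocytes below 75.000, not normalised after 7 days | yes |
| ALT/AST >5x ULN for more than 2 weeks | yes |
| ALT/AST >8x ULN | no |
| ALT/AST >3x ULN with total bilirubin >2x ULN | no |
| ALT/AST >3x ULN with symptoms or eosinophilia | no |

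The QTcF and thrombocyte criteria carry over essentially intact. Of four liver criteria, one carries over.

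**Step 2. Who can be counted.** To be withdrawn for the 8.3 liver reason, a subject must stay above 5x ULN for more than two weeks without first meeting another mandatory criterion. Broadly, that means 5x to 8x ULN, bilirubin not above 2x ULN, and none of the listed symptoms. Scheduled samples are about four weeks apart, so the duration is established by an unscheduled retest or at the next visit. The two omitted criteria can be met on a single sample. The exception is a subject who had already been above 5x ULN for more than two weeks before she worsened.

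**Step 3. What the count gives.** Outside that exception:

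| Withdrawals | Present bullet | With the two criteria added |
|---|---|---|
| Two for >8x ULN | 0 | 2 |
| Two for >3x ULN with bilirubin >2x ULN | 0 | 2 |
| One for each of the three criteria | 1 | 3 |

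**Step 4. Is there another study-level liver count?** Attachment 6 acts on the individual subject. Section 12.9 gives the sponsor a general right to terminate and names no liver trigger. The interim analysis (Section 9.1.6) is a single look at the first 16 of 80 subjects (16/80 = 20%), after their follow-up visit, with no liver threshold. None sets a number of cases.

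**Step 5. Illustration only.** The chance of two or more events among n subjects, each with risk p, is P = 1 − (1 − p)^n − n·p·(1 − p)^(n−1). Every p below is an assumption.

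- Active arm, n = 40, risk of an omitted criterion: p = 0.5% gives 1.7%; 1% gives 6.1%; 2% gives 19.0%; 5% gives 60.1%. This is how often two or more uncounted cases would arise.
- False triggers: the Definitions of Terms include placebo in study drug, so n = 80. For a combined background risk across the three criteria of 0.1%, 0.5% or 1%, the widened bullet would be met by chance in 0.3%, 6.1% or 19.1% of trials.

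**The case against.** The strongest reply is that nothing is contradicted and little is lost. Section 8.3 is permissive and does not call its list exclusive. Section 12.9 already allows the sponsor to stop, so a wider bullet adds a prompt and no new power. Which individual criteria become study-level triggers is a design judgement.

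The individual safeguards are also real. ALT and AST are screened at entry. A case meeting the Attachment 6 definition is reported within 24 hours, is worked up, and generally comes off treatment. A medically significant event can qualify as an SAE, with its own 24-hour route (Sections 10.1 and 10.7). Review at the first case may be tighter than a count of two.

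Most of this stands, and it limits the practical effect. It does not explain why a count that does exist should take the milder liver course and pass over the worse ones. Nor is the early reporting uniform: an isolated ALT above 8x ULN does not meet the Attachment 6 definition, so unless it is an SAE the withdrawal is notified within two days.

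The fourth liver criterion is also absent from 8.3. That is defensible, since fatigue or nausea with ALT above 3x ULN is much less specific. The two lists need not mirror each other in full.

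**Conclusion.** The gap is real, and the bullet should be changed. Two or more subjects withdrawn for ALT/AST >8x ULN, or for ALT/AST >3x ULN with bilirubin >2x ULN, would normally not meet the only liver rule in 8.3. This rests on reading 8.3 as written, by reason of withdrawal, and on 8.2 being applied promptly.

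Four stronger readings are not supported:

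- A reader might infer that 8.2 and 8.3 conflict. They do not: one governs subjects and the other the study.
- A reader might infer that two severe cases would go unnoticed, or that the study could not be stopped. Reporting, work-up and Section 12.9 all say otherwise.
- A reader might treat every 8.2 bilirubin case as the Attachment 6 signal. The attachment requires no other cause, no cholestasis and an excess over control; 8.2 requires none of these.
- A reader might take the Phase I record as zero liver events in 59 exposed subjects (41 men and 18 women, Section 1.5) and derive an upper limit of 1 − 0.05^(1/59) = 5.0%. Section 1.3 says only that laboratory abnormalities were not clinically relevant, which is not a documented liver count.

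The probabilities above therefore show scale under assumed risks. The conclusion does not depend on them.

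**What to change.** Reword the liver bullet of Section 8.3 so that the threshold of two or more subjects applies to withdrawals for any of three Section 8.2 criteria, in any combination: "ALT or AST >8x ULN"; a "confirmed increase in ALT or AST >5x ULN for more than 2 weeks"; or "ALT or AST >3x ULN and total bilirubin >2x ULN". Keep the statement that the study may, rather than must, be stopped.

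Do not add ALP, absence of another cause, or treatment arm as conditions for counting. Section 8.2 has none of them. Absence of another cause is a judgement made after a work-up and is assigned to no one. Such conditions would again separate the withdrawal reason from the counted reason. They belong in the review that the trigger prompts.

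The cost is one bullet in a protocol amendment, with no new data, visits or thresholds. The downside is an occasional review or pause set off by background or placebo cases.
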